1.2.4 Evaluate the PSA doubling time
Endpoint: Time elapsed from baseline PSA to double in value.

1.2.5 Evaluate overall survival at 2 years relative to the SWOG intermittent ADT historic cohort.
Endpoint: Patients will be followed for survival for two years after study enrollment

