2 BACKGROUND

Background: Prostate cancer is the most commonly diagnosed cancer in the United States and second leading cause of cancer death. At diagnosis, approximately 10% of men will have bone metastases identified on technetium bone scan [1]. These bone metastases can result in skeletal related events (SREs) causing substantial morbidity [2]. Men with five or fewer prostate cancer bone metastases noted on initial bone scan have a 94% 2-year survival rate, and a significantly favorable overall survival when compared to those with more lesions [3]. The current standard of care for men with overt metastatic disease is immediate androgen deprivation therapy (ADT) [4]. Long term androgen deprivation therapy results in a significant decrement in quality of life[5] and a host of unfavorable side effects including but not limited to loss of libido, lack of energy, difficulty concentrating, hot flashes, decreased bone density, decreased muscle mass, and increased risk of heart attack and stroke. Although ADT will delay the appearance of tumor related symptoms in metastatic patients, there are no data that it prolongs overall survival[4]. Developing novel strategies to control metastatic prostate cancer with side effect profiles superior to that of ADT or other approved systemic agents is highly desirable. External beam radiation treatment is effective at controlling both primary and metastatic prostate cancers, and Radium-223 has demonstrated a survival benefit in castrate-resistant prostate cancers. Both forms of therapy have been shown to palliate painful bony lesions.

Rationale for the combination of Radium-223 and External Beam Radiation: Radium-223 is a calcium-mimetic radiopharmaceutical that accumulates in bones and emits alpha radiation from Radium-223 decay and releases relatively high energy with a narrow range (2 to 10 cells)[5]. Following promising results in a phase II trial, the phase III ALSYMPCA trial was conducted in mCRPC with symptomatic bone metastases who either had received or were ineligible for docetaxel [6, 7]. Patients received 6 doses of Radium-223 50 kBq/kg intravenously every 4 weeks. A pre-planned interim analysis showed a significant 2.8-month median OS benefit compared to the placebo arm (14 vs. 11.2 months), which is anticipated to lead to regulatory approval [8]. An updated analysis

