9 STUDY CALENDAR

1 cycle = 28 days¹¹

Examination	Screening ¹	Neo-adjuvant C1	EBRT	C2 ⁷	C3	C4	C5	C6	End of Treatment ¹⁷	Follow-up ⁸
Informed consent	X									
Medical history	X									
Eligibility criteria	X									
Vital signs	X	X		X	X	X	X	X	X	
Physical examination ¹⁸	X	X		X	X	X	X	X	X	X
Karnofsky Performance Status or ECOG Equivalent (Appendix 17.5) ¹⁸	X	X		X	X	X	X	X	X	
Concomitant Medications ¹⁸	X	X	X	X	X	X	X	X	X	X
Adverse Events ¹⁴		X	X	X	X	X	X	X	X	X
Hematology ^{2, 13}	X	X ¹³		X ¹³	X					
Chemistry ^{3, 13}	X	X ¹³		X ¹³	X					
ECG ⁵	X									
CT or MRI ⁴	X								X	
Radium-223 ¹⁶		X		X	X	X	X	X		
EBRT			X							
PSA and Testosterone ^{9, 13}	X	X	X ⁹	X	X	X	X	X	X	X
Bone scans ⁶	X			X ¹²	X ¹²	X	X ¹²	X ¹²	X	X
QOL questionnaires	X		X ¹⁵			X			X	X
Myriad CCP ¹⁰	X									
Myriad HRD ¹⁰	X									

- 1 ALL Pre-study/Screening procedures should be completed within 4 weeks of study enrollment - with the exception of laboratory tests which need to be completed within 2 weeks prior to study enrollment, and imaging assessments which must be completed within 90 days of enrollment. Consent may be signed \leq 45 days prior to cycle one day one.
- 2 Hematology includes CBC with differential and platelets.
- 3 Chemistry includes Albumin, Alkaline Phosphatase, Aspartate Aminotransferase, Alanine Aminotransferase, Total Bilirubin, Calcium, Carbon Dioxide, Creatinine, Chloride, Glucose, Potassium, Protein, Sodium, Urea Nitrogen. 4 CT-based scans (either Fluciclovine PET/CT or diagnostic CT) or MRI that includes the chest, abdomen and pelvis. A similar imaging modality (MRI or CT-based) used at screening is preferred, but not required at follow up evaluation. Diagnostic CT at follow-up is sufficient if PET/CT was used at screening. Disease assessment to be conducted by PCWG2 and RECIST 1.1 section 10.1.1.
- 5 ECG will be done only if medically indicated.
- 6 Bone scans should be obtained between cycle 3 and 4 of the study dependent on any dose delays that may extend cycle time. Bone scans should be performed 2-4 weeks after the final Radium-223 dose. Bone scans will also be performed at any sign of progression as defined in section 10.
- 7 Cycle 2 may be delivered concurrently with external beam radiation to the primary site. Therefore, cycle 2 will NOT be delayed to allow completion of the external beam radiation.
- 8 Follow-up visits will occur every 3 months (+90/-30 days) for an approximate duration of two years from the time patients are enrolled on the study.

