10 CRITERIA FOR EVALUATION AND ENDPOINT

Assessment of clinical outcomes:

Clinical outcomes will be assessed at various time points from the start of protocol treatment. Patients will be followed for a total of 2 years after enrollment.

A study subject that completes Cycle 1 of Tadium-223, EBRT, and at least 3 cycles of Radium-223 will be considered evaluable.

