11 STATISTICAL CONSIDERATIONS

The primary objective is to determine the hormone-therapy-free survival time for men treated with concurrent EBRT and Radium-223 and determine whether 20% of subjects do not meet the progression endpoint and require ADT at 15 months. The primary outcome is 15 months hormone- (or other systemic) therapy-free survival. The null hypothesis is that 99% of subjects will start systemic therapy within 15 months. The alternative hypothesis is that 80% of subjects will start systemic therapy within 15 months. With 20 evaluable subjects there will be 93% power for this alternative hypothesis using an exact binomial test at the one-sided 0.05 significance level. The null hypothesis will be rejected if 2 or more out of 20 subjects are not placed on systemic therapy within one year.

One of the secondary endpoints is to determine the hormone-therapy-free survival time for men treated with concurrent EBRT and Radium-223 and determine whether it is a 30% risk reduction over the SWOG intermittent ADT historic cohort. This secondary hypothesis will be tested only if the primary null hypothesis is rejected. The outcome for

this secondary hypothesis is 15 month hormone- (or other systemic) therapy-free survival. In 2012 a SWOG cooperative group trial reported that 78% of subjects on intermittent androgen therapy had resumed ADT within 15 months, and this proportion will be used as a null hypothesis. With 20 evaluable subjects, and a null hypothesis that 78% or more of patients will start systemic therapy within 15 months there will be 80% power to detect an alternative hypothesis that 48% or fewer will start systemic therapy within 15 month using an exact binomial test at one-sided alpha =0.05 significance level.

Additional, secondary endpoints are time to first skeletal related event (SRE), overall survival, PSA doubling time, overall survival and toxicities. All secondary endpoints will be evaluated descriptively. Time to first SRE, OS, and PSA doubling time will be analyzed via Kaplan-Meier product limit methods and associated 95% confidence intervals. Toxicities will be tabulated using CTAE version 4.0. The number and proportion of subjects with toxicities will be reported.

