12 REGISTRATION GUIDELINES

Patients must meet all of the eligibility requirements listed in Section 5 prior to registration.

Study-related screening procedures can only begin once the patient has signed a consent form. Patients must not begin protocol treatment prior to registration.

Treatment should start within 21 working days after registration.

To register eligible patients on study, complete a Clinical Trials Office Patient Registration Form and submit to: [contact].

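### With 20 men and about 1 to 3 deaths expected, the planned Kaplan-Meier 95% limits for 2-year survival can collapse or just exclude the 85% comparator; exact limits and one fixed survival clock are needed

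*Combined protocol and SAP*

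**What the plan says.** Section 11 gives the analysis of survival in one sentence: "Time to first SRE, OS, and PSA doubling time will be analyzed via Kaplan-Meier product limit methods and associated 95% confidence intervals". It specifies no variance formula, no transformation and no fallback for few events. The same section says "All secondary endpoints will be evaluated descriptively".

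Objective 1.2.5 fixes the landmark and the comparator: "Evaluate overall survival at 2 years relative to the SWOG intermittent ADT historic cohort". Section 4.1 goes further and says the study will test whether treatment improves survival over that cohort.

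The sample size is 20 (Section 4.2). Section 2 gives two figures for 2-year survival. Men with five or fewer bone metastases on the initial scan "have a 94% 2-year survival rate". The minimal-disease men on the SWOG intermittent arm had 85%.

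On follow-up, the endpoint of 1.2.5 reads "Patients will be followed for survival for two years after study enrollment". Section 10 reads "Clinical outcomes will be assessed at various time points from the start of protocol treatment". Section 12 reads "Treatment should start within 21 working days after registration", whereas Section 7.2 places the first radium cycle at enrollment. Footnote 8 of the study calendar sets visits every 3 months, with a window of +90/-30 days, "for an approximate duration of two years from the time patients are enrolled on the study".

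**The concern.** Greenwood's variance is built from the observed deaths. With none it is zero, and with one or two the normal approximation behind the interval is poor. A trial of 20 men with a good 2-year prognosis falls in that range.

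The interval is the only planned measure of uncertainty for 2-year survival, and it will be read beside the historic figure. If it collapses at 100%, or if its lower limit stops just above 85%, a result compatible with no survival advantage looks like an improvement on the SWOG cohort.

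A second, smaller issue is whether every man is observed to month 24 on the clock used for the estimate.

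**Working it through.** **The plan's own figure.** No precision or expected number of deaths is stated for survival. The primary power is stated, and it reproduces: 1 - 0.80^20 - 20 x 0.20 x 0.80^19 = 1 - 0.0115 - 0.0576 = 0.931, against 93% in Section 11. That exact binomial test is not in question.

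**Inputs.** n = 20 (Section 4.2). True 2-year survival S = 0.85 and 0.94 (Section 2), with 0.90 added as a point between them. Follow-up is first taken as complete to 24 months, so the Kaplan-Meier estimate is (20 - d)/20 for d deaths and d is binomial(20, 1 - S).

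**Expected deaths.** 20 x 0.06 = 1.2; 20 x 0.15 = 3.0.

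**Chance of no deaths, S^20.** 0.94^20 = 29.0%; 0.90^20 = 12.2%; 0.85^20 = 3.9%.

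**Interval formulas.** Let s = (20 - d)/20 and g = sqrt(d / [20(20 - d)]).
- Plain: s ± 1.96 s g.
- Log: s exp(±1.96 g).
- Log-log: s raised to the power exp(±1.96 g/|ln s|).
- Clopper-Pearson: beta quantiles; with no deaths the lower limit is 0.025^(1/20) = 0.832.

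Upper limits are cut at 100%.

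| Deaths | Plain | Log | Log-log | Clopper-Pearson |
|---|---|---|---|---|
| 0 | 100-100% | 100-100% | undefined (ln 1 = 0) | 83.2-100% |
| 1 | 85.4-100% | 85.9-100% | 69.5-99.3% | 75.1-99.9% |
| 2 | 76.9-100% | 77.8-100% | 65.6-97.4% | 68.3-98.8% |
| 3 | 69.4-100% | 70.7-100% | 60.4-94.9% | 62.1-96.8% |

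**Apparent superiority when there is none.** If true survival is 85%, P(0 deaths) = 3.9% and P(1 death) = 20 x 0.15 x 0.85^19 = 13.7%, together 17.6%. In both outcomes the plain and log intervals lie wholly above 85%. A correct two-sided 95% interval should do that at most 2.5% of the time. The exact interval contains 85% in both outcomes.

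**Coverage.** This is the sum of the binomial probabilities of those d whose interval contains S. A zero-width or undefined interval counts as a miss.

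| True S | Plain | Log | Log-log | Clopper-Pearson |
|---|---|---|---|---|
| 94% | 70.4% | 70.9% | 68.1% | 99.4% |
| 90% | 87.6% | 87.6% | 83.5% | 98.9% |
| 85% | 81.9% | 82.3% | 93.9% | 97.8% |

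Between 85% and 94% the exact interval never covers less than about 97.5%.

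**Where the shortfall comes from.** At 94%, removing the zero-death outcome gives 70.4/71.0 = 99.2% for plain and 68.1/71.0 = 95.9% for log-log. At 85% the plain and log shortfall comes mainly from the one-death outcome, whose lower limits of 85.4% and 85.9% just miss 85%. This is a lattice edge: plain coverage is 95.2% at a true survival of 85.5%, and log coverage is 94.7% at 86%.

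**Follow-up.** If the window of -30/+90 days applies to a month-24 visit, last contact falls between about months 23 and 27. If contacts are spread evenly over that range (an assumption), a quarter of survivors are last seen before month 24: 0.25 x 85% = 21% to 0.25 x 94% = 23.5% of the men. In simulation this leaves coverage essentially unchanged (70% plain at 94%). If instead every last contact fell between months 23 and 24, the curve would end before month 24 in every run.

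**The case against.** The strongest reply is that survival is a descriptive secondary endpoint with no test, threshold or decision attached, and that Kaplan-Meier with 95% limits is conventional. Nobody would be misled by 20 of 20 alive with limits of 100% to 100%, because the failure is visible. Once at least one man has died, the plain and log intervals over-cover at most true values from 86% to 94%, and log-log can be longer than the exact interval.

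Much of this stands. A reader might infer that Kaplan-Meier intervals in this trial are generally too short. The documents do not support that: no interval type is named, and the low coverage at 94% is the zero-death outcome, not a shortfall across all outcomes. Whether an undefined log-log interval counts as a miss is also a convention.

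Two things survive the reply. A descriptive interval labelled 95% still has to mean that, particularly where 1.2.5 and Section 4.1 set it against a historic cohort. And the one-death intervals show no visible defect: 85.4-100% looks like an ordinary result that excludes 85%.

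On follow-up, a reader might infer that every man can be censored before month 24, leaving the estimate undefined there. That is too strong. The endpoint of 1.2.5 gives two years from enrollment, Section 7.2 starts cycle 1 at enrollment (which would remove any lag), the sentence in Section 10 is general and does not define the survival origin, and the window runs 90 days late as well as 30 days early.

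**Conclusion.** The concern holds for the 2-year survival interval. No common Kaplan-Meier form gives a usable interval with zero deaths, which has a 4% to 29% chance over the protocol's own survival range. With one death the plain and log forms exclude the 85% comparator, giving a 17.6% chance of apparent superiority if true survival is 85%. Choosing log-log alone repairs the one-death case but not the zero-death case.

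The figures assume 20 analysed men, complete follow-up to 24 months, true survival between 85% and 94%, and the minimal-disease figure of 85% as the SWOG comparator, since Section 2 gives no 2-year figure for the whole intermittent arm. The 82% coverage at 85% survival is sensitive to the exact true value; the zero-death problem is not.

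Some men may, not will, be censored before month 24, because the documents leave the time origin and the end of follow-up loose. None of this touches the primary endpoint or its power. It should be corrected, but it does not threaten the trial.

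**What to change.** In Section 11, state that 2-year survival, and any other Kaplan-Meier landmark proportion with few events, will be reported with exact 95% limits: Clopper-Pearson when 24-month status is known for all men, and the beta-product method when some are censored earlier. The Kaplan-Meier curve can stay as the display. The section already uses exact binomial tests, so this fits the rest of the plan.

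In 1.2.5, Section 10 and calendar footnote 8, state one time origin for survival and require vital status at or after 24 months from it. Reconcile Sections 7.2 and 12 on the interval between enrollment or registration and first treatment.

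The cost is one sentence of analysis text, one clarification of the origin, and a vital-status check from the record. The exact limits are conservative (about 97.5% to 99.4% coverage). They are wider than plain or log limits at zero to three deaths. Against log-log they are shorter with one or two deaths (24.7 against 29.8 points with one) and about equal with three (34.7 against 34.5).

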7.4 Duration of Therapy

Subjects must be withdrawn from the study treatment for the following reasons:

Patients are expected to receive one neo-adjuvant dose of Radium-223 followed by EBRT for 2 to 6 weeks followed by 5 additional cycles of Radium-223. The treatment phase of the study should be completed in approximately 6 months pending dose delay or discontinuation

- Subject withdraws consent from the study treatment and/or study procedures. A subject must be removed from the trial at his/her own request or at the request of his/her legally acceptable representative. At any time during the trial and without giving reasons, a subject may decline to participate further. The subject will not suffer any disadvantage as a result.
- Subject is lost to follow-up.
- Death.
- Disease progression as defined in section 10

- In the event of disease progression, the subject will no longer receive study treatment, but will remain on the study for all follow-up evaluations, which include indicated imaging studies, lab draws, and all questionnaires.

Subjects may be withdrawn from the study for the following reasons:

- The subject is non-compliant with study drug, trial procedures, or both; including the use of anti-cancer therapy not prescribed by the study protocol.
- If, in the investigator's opinion, continuation of the trial would be harmful to the subject's well-being.
- The development of a second cancer.
- Development of an intercurrent illness or situation which would, in the judgment of the investigator, significantly affect assessments of clinical status and trial endpoints.
- Deterioration of ECOG performance status to 4.

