- 9 PSA and Testosterone within 24 hours prior to or after starting external beam radiation.
- 10 Correlative studies are OPTIONAL; refer to section 14.1 for archival tissue instruction
- 11 Cycles should occur at least 28 days after the previous cycle and no more than 42 days after the previous cycle (0 to +14 days).
- 12 Bone scans are optional at the time points indicated by this superscript and will be performed if there is clinical suspicion of progression that falls outside the objective criteria of progression for this study.
- 13 All post-screening laboratory tests should be drawn approximately 7 days, but no fewer than 3 business days, before radium dosing. Laboratory tests for CBC differential platelets must have results available prior to radium ordering. Laboratory safety assessments MUST be performed and resulted prior to radium dosing.
- 14 The collection of all adverse events will begin after the first dose of study treatment and end 30 days after the last dose of study treatment. The collection of treatment related adverse events will continue until the last study visit (or until new cancer treatment is initiated, if sooner).
- 15 QOL Questionnaires should be completed on the final day of EBRT \pm 7days.
- 16 If a patient meets biochemical progression, the patient may continue to receive treatment, at the Investigator's discretion, until a validated PSA test has confirmed biochemical progression.
- 17 End of treatment visit will occur 28 days (\pm 7 days) after last treatment is administered.
- 18 Physical exam, KPS or ECOG equivalent, and concomitant medications do not need to be repeated if they have been performed less than 7 days prior.

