Exploratory endpoints are to evaluate if a commercially available cell-cycle progression gene assay (Myriad CCP) performed on the original prostate biopsy or surgical pathology specimen correlates with biochemical or clinical progression free survival in the study population.

Correlations with survival endpoints will be performed using exploratory Cox proportional hazards regression analysis.

Primary analysis and report planned at 15 months of follow up for all enrollees.

Health-related Quality of Life as scored by EPIC urinary, bowel, sexual, and hormonal domains, as well as PROMIS-29 questionnaires.

Medians, ranges, and quartiles will be computed for all health-related Quality of Life domains. Exploratory logrank tests will be used to relate domain scores to survival outcomes (hormone-free survival, time to first skeletal event, overall survival, and PSA doubling time).

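### Section 11 relates repeatedly measured QOL scores to survival by log-rank test without naming the visit or the grouping; the Cox regression already in that section would be a cheap improvement

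*Combined protocol and SAP*

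**What the plan says.** Section 11 (Statistical Considerations) introduces the topic as "Health-related Quality of Life as scored by EPIC urinary, bowel, sexual, and hormonal domains, as well as PROMIS-29 questionnaires". Two sentences of method follow. The first is descriptive: "Medians, ranges, and quartiles will be computed for all health-related Quality of Life domains". The second is the test: "Exploratory logrank tests will be used to relate domain scores to survival outcomes". The outcomes listed are "hormone-free survival, time to first skeletal event, overall survival, and PSA doubling time". Section 11 does not say which visit's score is used, how a score becomes a group, or whether a landmark or time-dependent method applies.

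Earlier in the same section, directly after the gene-assay endpoint, the plan states: "Correlations with survival endpoints will be performed using exploratory Cox proportional hazards regression analysis". That sentence does not mention QOL.

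The Study Calendar (Section 9) marks QOL at screening, EBRT, cycle 4, end of treatment and follow-up. A footnote adds "QOL Questionnaires should be completed on the final day of EBRT", and another says "Follow-up visits will occur every 3 months (+90/-30 days) for an approximate duration of two years". Under Section 7.4, men who progress stop study treatment but stay on study for follow-up evaluations, "which include indicated imaging studies, lab draws, and all questionnaires". Section 1.1 counts time to ADT from the start of study therapy.

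**The concern.** A conventional log-rank test compares groups. EPIC and PROMIS-29 domain scores are not groups, so someone must split them, and the plan does not say where. Splitting discards information in a study of 20 men. A split chosen after the outcomes are known raises the false-positive rate.

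The visit is also open. If men are grouped by a later score while time runs from the start of therapy, some groupings can only be reached by men who stayed event-free long enough to be scored. That is immortal time.

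A separate problem is reverse causation. Section 2 lists reduced libido, low energy and hot flashes among the effects of ADT, and the EPIC sexual and hormonal items in Appendix 17.2 ask about these. A score recorded after ADT begins may be a result of the hormone-free-survival event rather than a predictor of it.

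QOL is a named secondary objective (Section 1.2.2), so these associations may be reported. What is at stake is whether a reported association can be trusted as a hypothesis, not the trial's main conclusion.

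**Working it through.** **The plan's own figures.** Section 11 gives no power, cut-point or error rate for the QOL tests. The figures that fix N = 20 reproduce.
- Primary, at least 2 of 20 free of systemic therapy: power = 1 − 0.8^20 − 20 × 0.2 × 0.8^19 = 0.931 (stated 93%). Exact one-sided alpha = 1 − 0.99^20 − 20 × 0.01 × 0.99^19 = 0.0169.
- Secondary, 22% against 52% free: a rule of at least 9 of 20 gives power 0.802 (stated 80%) and alpha 0.0186.

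These set the number of men only and do not bear on the choice of test here.

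**Step 1: information kept by a median split.** For a normal score, the correlation between the score and the indicator of lying above its median is √(2/π). The share of information kept is the square, 2/π = 0.637, or about 64%. This is an asymptotic illustration. Normality of the EPIC and PROMIS-29 scores is assumed.

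**Step 2: simulation set-up.** These assumptions are not from the documents, except N = 20 and the 80% event rate of the alternative hypothesis:
- exponential event times with hazard −ln(0.2)/15 = 0.1073 per month;
- censoring at 24 months, giving a mean of 18.5 events;
- normal scores;
- two-sided 5% tests;
- 6,000 runs with scores unrelated to event time, and 5,000 runs per power figure.

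**Step 3: power, baseline score.**

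| Hazard ratio per SD | Median split | Continuous score |
|---|---|---|
| 1.65 | 32% | 47% |
| 2.0 | 50% | 71% |
| 2.7 | 72% | 91% |

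**Step 4: false-positive rate when the score is unrelated to outcome.**

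| Analysis | Rate |
|---|---|
| Baseline, continuous | 5.5% |
| Baseline, one median split | 6.3% |
| Baseline, best of the three quartile cuts | 17% |
| Baseline, free search for the best cut | 38% |
| Month-7 score, median split, only men still event-free then | 7.5% |
| Month-7 improvement, earlier events counted as not improved | 36% |
| Ever improved at any visit before the event | 40% |
| Month-7 score, all men, lowered by about 0.5 SD if the event came first | 12% |

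The first four rows show that the excess comes from searching over cuts, not from a single split fixed in advance. In the next three rows, immortal time is large for two groupings and largely absent when a fixed-visit score is used among men still at risk. The 7.5% is a small-sample excess with roughly 9 men. The last row is reverse causation, and the size of the fall is assumed.

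**Step 5: how often later scores follow the event.** By Section 11's own hypotheses, 0.80 × 20 = 16 men (alternative) to 0.99 × 20 = 19.8 men (null) start systemic therapy by 15 months, while QOL follow-up runs to about two years. Many later scores would therefore be taken after the event.

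**Step 6: what the better method can deliver.**
- Under a constant hazard, men still free of systemic therapy at month 7 number 20 × 0.2^(7/15) = 9.4 under the alternative and 20 × 0.01^(7/15) = 2.3 under the null.
- For overall survival, Section 2 quotes 2-year rates of 94% and 85% in other cohorts. If they applied here, deaths would be 20 × 0.06 = 1.2 to 20 × 0.15 = 3.0.
- Four EPIC domains, seven PROMIS-29 domains and one pain-intensity item against four outcomes make 12 × 4 = 48 tests per visit. At 5% each, 48 × 0.05 = 2.4 false positives are expected whichever test is used.

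**The case against.** The strongest reply is that the plan describes none of the harmful choices.

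A reader might infer that a log-rank test forces arbitrary cut-points. It does not. A median or quartile split could be fixed in advance, and the summaries already planned would supply one, although the plan does not say they define the groups. A single median split has a false-positive rate near nominal (6.3%). The log-rank test also has a form for a continuous covariate, the score test of a Cox model. The 17% and 38% figures need a search over cuts that the plan does not mention. This part of the reply stands: the fault is that the grouping is left open.

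A reader might also infer that immortal-time bias is built in. The documents do not support that. Section 11 never says post-baseline scores will be used, a screening score carries no immortal time, and a fixed-visit score among men still at risk largely avoids it. The 36% and 40% figures belong to groupings that the plan does not name. This also stands: the bias is possible, not inherent.

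Finally, the 64% should not be turned into a loss of seven of the 20 men. It is asymptotic, it assumes normal scores, and information in a survival analysis follows events rather than men.

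The remaining argument is that choosing Cox over log-rank for an exploratory look is mere preference. That does not stand. Section 11 already contains the method, and keeping the score continuous recovers power and removes the cut-point question.

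**Conclusion.** The point holds as a cheap improvement. Section 11 plans log-rank tests on multi-level, repeatedly measured scores and names neither the assessment nor the grouping. Splitting the scores costs information: about 64% is kept in the asymptotic normal case, and power falls from 71% to 50% at a hazard ratio of 2 per SD in the assumed scenario. The silence on grouping leaves cut-points open to choice after the data are seen. The silence on timing allows immortal-time bias if post-baseline scores are used with time from treatment start, and reverse causation if scores taken after ADT starts are included.

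The sizes rest on the simulation assumptions above (exponential times, 80% events by 15 months, normal scores). They show what could happen, not what the plan commits to. The analysis is labelled exploratory and carries no error-rate claim. The formal tests of 15-month therapy-free survival are untouched.

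**What to change.** Replace the log-rank sentence in Section 11 with wording to this effect:
- Associations between QOL domain scores and each survival outcome will be explored by Cox regression, with the screening domain score as a continuous covariate.
- Post-baseline scores will be used only in one of two ways: from a stated landmark (for example the end-of-treatment visit) among men still free of the event in question, with time counted from the landmark; or as time-dependent covariates using only scores recorded before the event.
- Scores taken after ADT or other systemic therapy starts will not be used as predictors of hormone-free survival.
- Results will be reported as hypothesis-generating, with the number of men and events in each model.

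The cost is a change of wording. No new patients, visits or data are needed. The downside is that landmark analyses will be small (roughly 2 to 9 men at month 7 for hormone-free survival under the plan's two hypotheses and a constant hazard). Overall survival will probably have too few deaths for any model to be informative, and the plan could say that this outcome will only be described.
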